Precis: A total of 40 patients taking proton pump inhibitors (PPIs) who undergo transjugular intrahepatic portosystemic shunt (TIPS) creation as part of routine clinical care will be randomized in 1:1 fashion to either continue or discontinue their PPIs to determine whether these commonly used gastric acid suppressing agents increase risk of post-TIPS hepatic encephalopathy (HE). Patients will be assessed for symptoms of minimal HE (MHE), using the established psychometric hepatic encephalopathy score (PHES) battery of tests. MHE assessment will be conducted at two timepoints: at baseline prior to randomization and TIPS creation and approximately 4 weeks after randomization and TIPS creation. Stool samples will also be collected at both timepoints to allow characterization of the gastrointestinal (GI) tract microbiome using 16S rRNA sequencing. The pre to post-TIPS change in PHES scores will be compared between patients randomized to continue versus discontinue their PPIs. Quality of life (QOL) will also be assessed. Changes in the GI tract microbiome will be analyzed to determine whether this represents a potential biological mechanism linking PPI use with post-TIPS HE.

Objectives: The primary objective is to determine whether discontinuation of PPIs reduces the risk of post-TIPS HE. Additional secondary objectives will include a comparison of cirrhosis-specific and gastroesophageal reflux disease-specific QOL in the PPI continuation and discontinuation groups. An exploratory objective is to determine whether PPI induced changes in the GI tract microbiome represent a potential biological mechanism mediating PPI-induced risk of post-TIPS HE.

Endpoints: Change in PHES pre to post-TIPS by intention-to-treat (ITT) (primary endpoint). Per-protocol change in PHES; change in Chronic Liver Disease Questionnaire (CLDQ) and Quality of Life in Reflux and Dyspepsia (QOLRAD) scores pre to post-TIPS (secondary endpoints). Mediation analysis of GI tract bacterial taxon abundances as a potential link between PPI use and post-TIPS HE (exploratory endpoint).

Population: 40 male and female Duke University Hospital patients over the age of 18 taking PPIs and undergoing TIPS placement as part of routine clinical care

Phase: 2

[figure not shown]
Number of Sites Enrolling Participants: 1

Description of Study Intervention: Patients will be randomized to receive instructions to stop their existing PPI therapy (experimental/discontinuation/deprescribing arm) or to receive no specific instructions regarding PPI therapy (control/continuation arm)

Study Duration: Approximately 24 months

Participant Duration: Approximately 6-8 weeks

Schematic of Study Design

1 Key Roles

Principal Investigator:

[name]. Ph.D.

Duke University Medical Center

[name]

[name]

Email: [contact]

[contact]

Lead Clinical Research Coordinator:

[name], C.R.C.

Duke University Medical Center

[name]

[name]

Email: [contact]

[contact]

2 Introduction: Background Information and Scientific Rationale

2.1 Background Information

Transjugular intrahepatic portosystemic shunt (TIPS) creation is an important minimally invasive procedure for treatment of complications resulting from cirrhosis and portal hypertension (1). Despite the beneficial effects of TIPS on ascites, gastrointestinal (GI) variceal bleeding risk, and in certain settings survival (2, 3), development of hepatic encephalopathy (HE) after TIPS can limit use of this procedure. HE is the most common complication of TIPS, occurring in 30% to 60% of patients (4). Medical therapy for HE, though effective, can be expensive (5) and cause unpleasant side effects (6). Thus, in patients who experience post-TIPS HE, the reduction in quality of life (QOL) can negate other beneficial effects of TIPS (7, 8). Furthermore, the cost of HE related care is substantial, estimated at \$5,370-\$50,120 per patient per year (9). Therefore, additional strategies to reduce the risk of post-TIPS HE are needed.

Recent retrospective studies have shown an association between proton pump inhibitor (PPI) use and HE in cirrhotic patients (10-20). Meta-analyses have supported a small but significantly increased risk of HE among cirrhotic patients taking PPIs, with pooled odds ratios ranging from 1.50 to 2.58 (21-24). Among these studies, two focused exclusively on TIPS patients and described a more robust effect size in this high risk population with a greater than 3 fold increased risk of post-TIPS HE among PPI users (19, 20). In an independent, unpublished dataset of 86 TIPS patients, we have further replicated the dose dependent association between PPI use and post-TIPS HE (Figure 1).

[figure not shown]

Figure 1: Patient timelines after TIPS showing intervals of PPI use and episodes of HE (left panel). Incidence rate ratios showing statistically significantly increased rates of post-TIPS HE with PPI use (middle panel) and with increasing PPI dosages (right panel).

Biological mechanisms to account for the association between PPI use and HE remain unknown, but a potential pathway involves alterations in the GI tract microbiome. Randomized placebo controlled studies have demonstrated that PPI use leads to distinct changes in the microbiome (25). These changes, characterized by colonization of the lower GI tract by oral flora not destroyed in a more alkaline stomach, appear to be reversible upon discontinuation of PPIs (25, 26). Separate observational studies have characterized the differences in GI flora

between cirrhotic patients with HE versus those without HE (27). In patients with HE, reduced levels of Lachnospiraceae, Ruminococcaceae, and Clostridiales and increased Enterobacteriaceae and Streptococcaceae closely mirror the changes caused by PPI use (25, 27). Thus, given the concordant changes in the lower GI tract microbiome seen with PPI use and in patients with HE, these bacterial taxa could play a role in mediating HE. However, other mechanisms, such as a simple effect of pH, are also plausible. Lactulose, long established as an effective treatment for HE, is a colonic acidifying agent (28). In a reduced pH environment in the colon, ammonia is protonated to the less well absorbed ammonium ion, which is thus excreted (28). By raising luminal pH, PPIs may counteract this process.

PPIs are among the most commonly used medications, but a Cochrane review has reported that 25% to 70% of patients may be prescribed a PPI inappropriately (29). Among TIPS patients, 60% to 75% take PPIs (19, 20). While short courses of PPIs are indicated for ulcer disease (30, 31) and possibly for prevention of esophageal variceal band ligation ulcers (32), PPIs do not appear in practice guidelines for prevention and management of portal hypertensive bleeding in cirrhotic patients (33). Thus, discontinuation of inessential PPI therapy in cirrhotic patients undergoing TIPS creation may be a simple and cost effective intervention to reduce the risk of post-TIPS HE.

Since the link between PPI use and HE is based solely on retrospective, observational data and because biological mechanisms remain unexplored, this protocol proposes a prospective, randomized study design to more definitively support or refute a role for PPI use as a risk factor for HE. Such a study design would more clearly determine whether discontinuation of PPI therapy can reduce the risk of post-TIPS HE and may also provide mechanistic insights into the interplay between upper GI tract pH, the GI tract microbiome, and HE.

2.2 Rationale

[figure not shown]
Rationale for a randomized trial

The rationale for this proposed prospective, randomized deprescribing trial is that currently available retrospective data implicating PPI use in post-TIPS HE are inadequate to justify discontinuation of PPIs. This is based on three considerations. First and foremost, retrospective data are unable to support causal conclusions. Therefore, the observation that TIPS patients taking PPIs experience higher rates of post-TIPS does not imply that discontinuation of PPIs would reduce rates of HE in these patients. Second, a Cochrane review of randomized PPI deprescribing trials described increased rates of gastroesophageal reflux disease (GERD) symptoms in patients who stopped their PPIs (29). Therefore, even if PPI use is causally linked to increased risk of post-TIPS HE, the harmful effects from worsening GERD in patients discontinuing PPIs may outweigh the beneficial reduction in post-TIPS HE. Third, retrospective observational studies provide few insights into biological mechanisms. Therefore, even if discontinuation of PPIs was known to be beneficial, this narrow strategy would fail to advance the understanding of physiologic connections between upper GI tract pH, the GI tract microbiome, and HE.

Rationale for microbiome analysis

In addition to better establishing causality and better assessing the potential benefits and risks of deprescribing PPIs to prevent HE, the proposed prospective, randomized study design will allow further analyses to dissect the role of the GI tract microbiome in HE. The proposed study seeks to further evaluate the role of the GI tract microbiome via statistical mediation analysis as illustrated in Figure 2 (34). Scenario A depicts a direct effect of PPIs on HE. Scenario B depicts simple mediation. The microbiome is considered a mediator if (1) PPIs are causally related to HE (i.e. $c \neq 0$ in scenario A), (2) PPIs are causally related to microbiome change (i.e. $a \neq 0$ in scenario B), and (3) the microbiome significantly predicts HE after controlling for PPI use (i.e. $b \neq 0$ in scenario B). Complete mediation is said to occur if $c' = 0$ (i.e. the impact of PPI use on HE is driven entirely through changes in the microbiome), whereas partial mediation is said to occur if $c' \neq 0$ (i.e. PPIs affect the risk of HE both through the microbiome but also through other unexplained mechanisms, such as a direct effect of pH). Formal statistical methods for quantifying such relationships in mediation analysis have been described (34).

Figure 2: Arrows demonstrate directionality of hypothesized causal chains linking PPI use, the microbiome, and post-TIPS HE.

Rationale for a deprescribing trial

This protocol proposes a randomized deprescribing study design, whereby patients who are already taking PPIs are randomized to continue or discontinue their PPI. Because currently available retrospective data suggest PPIs may increase risk of HE, it would be potentially unethical to administer PPIs to patients not already on these agents. In contrast, a deprescribing trial, where patients are randomized to continue or discontinue a potentially ineffective or harmful medication, can be considered in such circumstances (35). Such deprescribing trials are well accepted in the field of geriatrics to combat polypharmacy and reduce pill burden, and PPIs have been the focus of multiple deprescribing trials (29).

Rationale for studying TIPS patients

This study focuses on deprescribing PPIs in the subset of cirrhotic patients undergoing TIPS creation. While a PPI deprescribing trial could be considered in cirrhotic patients in general or in other patient subsets, HE represents an acute clinical problem in TIPS patients and prevention and management of HE in this group remains a challenge (36). Retrospective studies have shown greater than 3 fold higher rates of HE associated with PPI use among TIPS patients (19, 20), compared with 1.50 to 2.58 fold higher rates among cirrhotic patients in general (21-24).

Therefore, TIPS patients may be more likely to enjoy benefits related to reduction in HE that outweigh the risks of worsening GERD symptoms.

2.3 Potential Risks and Benefits

2.3.1 Known Potential Risks

Adverse reactions to abrupt discontinuation of PPIs have been characterized in a deprescribing trial conducted in 164 patients age 65 and older with a history of acute grade I-III esophagitis (37):

- GERD: heartburn (54.8% in discontinuation arm vs 8.3% in PPI continuation arm), acid regurgitation (41.9% vs 12.5%)
- Esophagitis documented by endoscopy: 69.6% vs 20.4%
- Other rare adverse events (AEs) occurring in both arms: glossitis, headache, diarrhea, cardiac arrhythmia, urticaria, abdominal pain, impotence, dysuria, leukopenia, pruritus, dizziness

Patients with gastric or duodenal ulcers, grade IV esophagitis (deep ulcer or esophagitis with complications) were excluded from this study. No ulcers, complications from esophagitis, or cases of grade IV esophagitis were reported in the discontinuation arm.

2.3.2 Known Potential Benefits

Potential benefits of PPI discontinuation include reduction in post-TIPS HE symptoms and decreased pill burden.

3 Objectives and Purpose

Primary objective: To determine whether discontinuation of PPIs in patients undergoing TIPS creation reduces the risk of post-TIPS HE, as assessed by psychometric hepatic encephalopathy score (PHES) tests of minimal hepatic encephalopathy (MHE).

Secondary objectives: To determine whether discontinuation of PPIs impacts chronic liver disease or GERD related QOL, as assessed by the Chronic Liver Disease Questionnaire (CLDQ) and Quality of Life in Reflux and Dyspepsia (QOLRAD) surveys.

Exploratory objectives: To perform mediation analysis to determine whether the relationship between PPI use and post-TIPS HE is driven by changes in the GI tract microbiome, characterized through 16S rRNA sequencing of stool samples.

4 Study Design and Endpoints

4.1 Description of the Study Design

The proposed study is a single center randomized, open-label, deprescribing trial of PPI users undergoing TIPS creation. The study will involve two arms: the experimental/PPI discontinuation arm will be instructed to stop taking their PPIs prior to TIPS creation and the control/PPI continuation arm will receive no special instructions regarding their preexisting PPI medication. Patients will be assessed for MHE using the PHES test battery and for QOL using the CLDQ and QOLRAD surveys prior to randomization, and approximately 6-8 weeks later after TIPS creation. Stool samples will be collected at both time points. After the second and final assessment approximately 4 weeks after TIPS creation patients will have completed the study.

4.2 Study Endpoints

4.2.1 Primary Endpoint

The primary endpoint of this study will be an intention-to-treat (ITT) analysis of the change in PHES pre versus post-TIPS, compared between the PPI continuation and discontinuation arms.

4.2.2 Secondary Endpoints

Secondary endpoints of the study will include a per-protocol analysis of the change in PHES pre versus post-TIPS in the PPI continuation versus discontinuation arm; an ITT analysis of the change in CLDQ and QOLRAD scores pre versus post-TIPS in the PPI continuation versus discontinuation arms; episodes of overt HE, defined as a West-Haven score greater than or equal to 2 (e.g. gross disorientation, drowsiness, asterixis, and inappropriate behavior), on-demand use of histamine H2 blockers or PPIs due to GERD symptoms, and AEs.

4.2.3 Exploratory Endpoints

As an exploratory endpoint, the GI tract microbiome will be characterized by 16S rRNA sequencing of stool samples at both time points. The change in bacterial taxon abundances pre versus post-TIPS will be estimated in each patient. Statistical mediation analysis will be used to explore whether PPI use impacts the risk of HE through changes in the GI tract microbiome (Figure 2).

5 Study Enrollment and Withdrawal

5.1 Participant Inclusion Criteria

In order to be eligible to participate in this study, an individual must meet all of the following criteria:

- Undergoing TIPS creation as part of routine clinical care
- On PPIs therapy (at least 20 mg omeprazole equivalent daily)
- Provision of signed and dated informed consent form by participant or legal representative
- Stated willingness to comply with all study procedures and availability for the duration of the study
- Male or female, age greater or equal to 18

Women and members of minority groups and their subpopulations will be offered the opportunity to participate in the study in accordance with the NIH Policy on Inclusion of Women and Minorities as Participants in Research Involving Human Subjects. The following PPI doses are considered equivalent: omeprazole 20 mg, lansoprazole 30 mg, pantoprazole 40 mg, esomeprazole 20 mg, and dexlansoprazole 30 mg (38, 39).

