5.2 Participant Exclusion Criteria

An individual who meets any of the following criteria will be excluded from participation in this study:

- Grade IV esophagitis or gastric or duodenal ulcer
- Recent endoscopic esophageal variceal band ligation necessitating PPI therapy for prevention of banding ulcer
- Zollinger-Ellison syndrome
- Active Helicobacter pylori infection
- Pregnancy

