10.2 Statistical Hypotheses

Primary endpoint: The null hypothesis is that there is no difference between PPI continuation and discontinuation groups in the change in PHES pre versus post-TIPS. The alternative hypothesis is that there is a difference in the change in PHES pre versus post-TIPS in the PPI continuation and discontinuation groups:

$$H_0: \mu_{+PPI} = \mu_{-PPI} \text{ versus } H_1: \mu_{+PPI} \neq \mu_{-PPI}$$

Here μ_{+PPI} represents the mean difference in PHES among patients in the PPI continuation arm, and μ_{-PPI} represents the mean difference in PHES among patients in the PPI discontinuation arm.

Secondary endpoints:

- Per-protocol evaluation of PPI deprescribing on post-TIPS HE: The null hypothesis is that there is no difference in the change in PHES among patients who adhered with PPI discontinuation instructions versus those who continued to use PPIs.
- ITT analysis of the change in CLDQ and QOLRAD scores: The null hypothesis is that there is no difference in the pre to post-TIPS change in CLDQ/QOLRAD scores among patients in the PPI discontinuation arm compared to patients in the PPI continuation arm.
- Episodes of overt HE: The null hypothesis is that there is no difference in the number of patients experiencing an episode of overt HE, defined as a West-Haven score greater than or equal to 2, in the PPI discontinuation arm compared to patients in the PPI continuation arm.
- On-demand requirement for acid suppression therapy: Descriptive statistics will be presented on the number of patients in the PPI discontinuation arm reporting on-demand use of histamine H2 blockers or PPIs.
- Adverse events: The null hypothesis is that there is no difference in the number of patients experiencing an AE in the PPI discontinuation arm compared to patients in the PPI continuation arm.

Exploratory endpoints:

For analyses exploring the role of the microbiome in mediating PPI induced post-TIPS HE, the null hypothesis is that $b = 0$ and that $c = c'$ (no mediation, see Figure 2). The alternative hypothesis is that $b \neq 0$ and $c' < c$ (partial or complete mediation) (34).

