10.4.6 Baseline Descriptive Statistics

Baseline characteristics of the PPI continuation and discontinuation arms will be compared, including demographics, comorbidities, prior HE and anti-HE therapy, and TIPS procedure characteristics, using means and ranges for continuous variables and counts and percentages for categorical variables. Inferential tests to assess differences in baseline characteristics of the

groups will be performed using T-tests for continuous variables and Fisher's exact tests for categorical variables.

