10.6 Measures to Minimize Bias

10.6.1 Enrollment/Randomization/Masking Procedures

Randomization codes will be generated and maintained by the PI. Randomization of subjects between the PPI continuation and discontinuation groups will be performed in a 1:1 fashion. The patient and treating IR physician will not be blinded (open-label design). The CRC performing MHE assessments via PHES tests and QOL assessments via the CLDQ and QOLRAD surveys will be blinded to patient assignment.

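### Current or prior HE is neither balanced nor adjusted for, and the overt-HE endpoint has no start time and no new-or-worsening rule, so HE ongoing at baseline could be counted in its Fisher test

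*Combined protocol and SAP*

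**What the plan says.** **Eligibility.** Section 5.1 accepts "Provision of signed and dated informed consent form by participant or legal representative". Section 5.2 opens with "An individual who meets any of the following criteria will be excluded from participation in this study" and lists five items: severe esophagitis or ulcer, recent banding that needs a PPI, Zollinger-Ellison syndrome, active H. pylori and pregnancy. None concerns HE, whether current, past or treated.

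**Baseline.** Section 10.4.6 compares the arms on characteristics "including demographics, comorbidities, prior HE and anti-HE therapy, and TIPS procedure characteristics", descriptively and with T-tests and Fisher's exact tests. Nothing carries these variables into an outcome analysis.

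**Allocation.** Section 10.6.1 says "Randomization of subjects between the PPI continuation and discontinuation groups will be performed in a 1:1 fashion" and names no stratification factor.

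**Overt HE.** Section 4.2.2 gives the endpoint as "episodes of overt HE, defined as a West-Haven score greater than or equal to 2". Section 10.2 tests for "no difference in the number of patients experiencing an episode of overt HE, defined as a West-Haven score greater than or equal to 2", and 10.4.3 uses a two-sided Fisher's exact test on the proportion with one or more episodes. None of the three gives a date from which episodes count, or says how an episode already under way is handled.

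**Primary analysis.** Section 10.4.2 applies an unadjusted two-sided T-test to post-TIPS minus pre-TIPS PHES.

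**The concern.** The trial asks about HE after TIPS, yet a patient with HE on Day 0 may be randomised. Randomisation is on Day 1 and TIPS on about Day 14 (7.3.7), so the text leaves two kinds of episode undecided: those ongoing at entry, and those starting between randomisation and TIPS. If they are counted, both arms gain events that TIPS did not cause, and the difference the Fisher test looks for shrinks.

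Resolved or treated HE is a separate matter. It is not an event, but it is plausibly prognostic. With 20 patients per arm it may fall unevenly, and neither the design nor the analysis corrects for that.

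Section 10.1 says there will be no separate analysis plan, so these rules have no other document to go in. In an open-label trial, deciding which episodes count after the data are seen is best avoided.

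**Working it through.** **1. Do neighbouring rules close the gap?**

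- Section 8.3 treats conditions present at screening as baseline unless they deteriorate, but this governs adverse-event reporting.
- Section 7.3.3 sets a window of 30 days after TIPS, also for adverse events.
- Section 8.1 names overt HE separately from drug-related adverse events, so neither rule plainly carries over.
- Section 7.3.7 schedules no West-Haven assessment at any visit, so there is no planned baseline grade to compare with.

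**2. The plan's own figure.** Section 10.5 states 71% to 96% power for change in PHES with 20 per arm. It gives no SD, so the figure cannot be reproduced, only back-solved. With a two-sided 0.05 t-test it corresponds to standardised differences of 0.82 to 1.20. No power is stated for the overt-HE test.

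**3. Dilution of the overt-HE test.** Let p be an arm's rate of new post-TIPS episodes and q the share of each arm in overt HE at entry and counted as events. The observed rate is p' = q + (1 − q)p, and the difference between arms shrinks by the factor (1 − q).

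Inputs: 20 per arm, two-sided 0.05. The control rate of 45% is the middle of the 30% to 60% in 2.1, which is for HE in general, so applying it to overt HE is an assumption. The 15% applies the roughly three-fold risk in 2.1 in full. The documents give no q. Exact power:

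| q (assumed) | Continue | Stop | Difference | Fisher power |
|---|---|---|---|---|
| 0 | 45.0% | 15.0% | 30 points | 44% |
| 10% | 50.5% | 23.5% | 27 points | 32% |
| 20% | 56.0% | 32.0% | 24 points | 22% |
| 30% | 61.5% | 40.5% | 21 points | 16% |

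From q = 0 to q = 30%, power falls from 24% to 8% at a 30% control rate and from 65% to 31% at 60%. If three-fold is read as an odds ratio, the falls are 17% to 6%, 26% to 10% and 27% to 15% at control rates of 30%, 45% and 60%. Type I error stays at about 0.02 (checked at a 45% rate). The harm is lost power, not false positives.

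**4. Chance imbalance in prior HE.** If K of 40 patients have prior or treated HE, the number X in one arm of 20 follows P(X = x) = C(K, x) C(40 − K, 20 − x) / C(40, 20), and the arms differ by |2X − K|. K is assumed.

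| K of 40 | Differ by 4 or more | Differ by 6 or more |
|---|---|---|
| 8 | 24% | 4% |
| 12 | 30% | 8% |
| 16 | 33% | 11% |
| 20 | 34% | 11% |

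A difference of 4 is 4/20 = 20 percentage points. If prior HE shifted the change in PHES by 1 SD (assumed), the estimate would move by 0.20 SD in either direction, or 0.20/0.82 = 24% of the smaller back-solved effect.

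**5. Stratify, adjust, or both?** In simulation with that 1 SD effect and a true difference near 0.82 SD, stratifying but keeping the unadjusted T-test gives power of about 64% and type I error of about 3%. The test is conservative because it ignores the balance gained. Adjusting for the factor gives about 70%. Stratification therefore needs the matching analysis.

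**The case against.** The best defence is that context already points to post-randomisation or post-TIPS events. The objective in section 3 concerns post-TIPS HE, arms exist only from Day 1, and a patient experiencing an episode in an arm reads naturally as a later event. A reader might infer from the open wording that baseline HE *is* counted in the test of post-TIPS HE. The documents do not support that. The overt-HE text permits it without directing it, and the primary endpoint subtracts the baseline PHES. What stands is that the rule is unwritten.

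Second, patients in overt HE may rarely reach randomisation. Section 10.5 draws on elective TIPS, enrolment is at a clinic visit, and 5.1 requires stated willingness to comply with procedures, which include paper tests. This is fair, and q may be small. But no rule says so, and 5.1 provides for surrogate consent. It is also tempting to argue that patients entering with HE have no room to worsen on PHES and improve in either arm. The plan gives no PHES range and no recovery data, so this stays a possibility.

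Third, randomisation keeps the tests valid, and stratification is partly a matter of preference. That is correct: a difference of 4 or more is not the usual outcome, since 66% to 76% of trials would be closer. The argument for acting is precision and interpretability at low cost.

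**Conclusion.** The point holds in two parts. First, the overt-HE endpoint lacks a start time and a new-or-worsening rule, so ongoing baseline HE could enter its Fisher test. At assumed rates of 45% versus 15%, that would cut power from 44% to between 32% and 16% for assumed baseline shares of 10% to 30%. If no one enters in overt HE, this loss is zero. Second, prior or treated HE is expected but neither balanced nor adjusted for. A difference of 4 or more patients arises in 24% to 34% of trials if 8 to 20 of 40 have it.

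The baseline shares and the 1 SD prognostic effect are assumptions, because the documents give neither. It does not follow that the primary test is invalid or that type I error is inflated. Nor does it follow that patients with HE must be excluded. That is an eligibility trade-off in a trial expecting about 20 eligible patients a year for about 24 months, which is nearly all of the 40 it needs.

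**What to change.** 1. In 4.2.2 and 10.4.3, count overt HE only if it is a new episode after TIPS or a worsening after TIPS from a West-Haven grade recorded on Day 0. List episodes between randomisation and TIPS separately.
2. In 10.6.1, stratify the 1:1 randomisation by prior overt HE or current HE medication (yes/no). In 10.4.2, replace the unadjusted T-test with a linear model of PHES adjusted for baseline PHES and that factor.
3. Reconcile 5.1, which lets a legal representative give consent, with 13.3.2, which has the participant sign.

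**Cost.** A Day 0 West-Haven grade must be added to the schedule in 7.3.7 and to the CRF. This is a new data item, though a small one. A two-stratum list must be kept, with variable block sizes to limit predictability in an open-label, single-centre trial whose PI holds the codes. No additional patients are needed and no new exclusion criterion is proposed.
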